## 1. Study Protocol

In this study, a double-blind randomized experimental design was used to allow subjects to take six months of health supplements (experimental group) and six months of placebo (control group) to see their effects on fatty liver, liver fibrosis and metabolic indicators.

First ask the patient to agree to participate in the trial and fully understand the content of the project. After the eligible subjects are evaluated and confirmed to be able to participate in the trial, they will take health care products daily according to the research setting (3 tablets before breakfast, 3 tablets before dinner, total 6 tablets ), at the first time of the test, 4 weeks, 8 weeks, 12 weeks, 16 weeks, and 24 weeks respectively to check blood and biochemical values, including creatinine (Cr), liver function index (AST, ALT), pre-meal blood sugar (AC) , And use Fibroscan to detect fatty liver and liver fibrosis. At the first time of the test, 4 weeks, 12 weeks, 12 weeks, 12 weeks, and 24 weeks, return to check blood routine / white blood cell classification examination (CBC/DC), uric acid (UA), cholesterol blood fat (HDL, LDL), triglyceride (TG), lipid Adiponectin/Leptin (Adiponectin/Leptin), C-reactive protein (CRP), insulin (Insulin); In addition, at the first, 12 weeks, and 24 weeks of the test, the metabolic indicators related to glycosylated hemoglobin (HbA1c) were tested.

This study will extract the follow-up data of subjects' return visits for analysis and research. The follow-up methods are phone reminders two weeks before the start of the trial, and reminders during monthly visits, asking about taking status, etc., to increase the subjects' compliance.

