#### SCHEDULE OF EVENTS

## 3. Statistical Analysis Plan

This study is expected to include a total of 60 people with non-alcoholic fatty liver disease, divided into two groups, 30 people in each group, double-blind randomized test. The primary end point (primary end point) is to see the severity of changes in the patient's steatohepatitis and fibrosis. The secondary end point is the degree of change in the patient's weight and lipid profile. Continuous variables are presented in normal probability plots and Shapiro-Wilk test evaluation. The relationship between variables Connectivity is analyzed by Pearson's correlation, and the Intra-intervention comparison is performed by Paired t test. Unify The calculation software is based on R software version 2.11.1.

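### FibroScan is measured at the first visit in both arms, but Section 3 plans no baseline-adjusted supplement-versus-placebo estimate

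*Combined protocol and SAP*

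**What the plan says.** Section 1 (Study Protocol) describes a two-arm, blinded, placebo-controlled randomised trial of six months. It specifies the instrument: "And use Fibroscan to detect fatty liver and liver fibrosis". The schedule in Section 2 shows FibroScan for both arms (A and B) at the first visit and at weeks 4, 8, 12, 16 and 24. HDL, LDL and triglycerides are also drawn at the first visit in both arms.

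Section 3 describes the sample as "divided into two groups, 30 people in each group, double-blind randomized test". The primary end point "is to see the severity of changes in the patient's steatohepatitis and fibrosis". The secondary end point is change in weight and lipids.

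The methods named in Section 3 are normality checks, a correlation analysis ("Connectivity is analyzed by Pearson's correlation") and one comparison ("the Intra-intervention comparison is performed by Paired t test"). It names no two-sample test, covariate, ANCOVA or repeated-measures model, and gives no alpha, power, effect size, standard deviation or correlation.

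**The concern.** The trial collects a baseline value of its imaging measure in every patient. The only planned use of that value is as one side of a paired difference, and that difference is tested within an arm. The randomised comparison is therefore not estimated at all, and no baseline adjustment is planned for it.

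The likely repair is a two-sample t test on the paired changes, since the end point is worded as change and the plan already forms those differences. That would supply a between-arm estimate but keep an inefficiency. Subtraction fixes the slope of follow-up on baseline at 1. With equal standard deviations the best linear slope is rho, which is below 1 whenever the measure is not perfectly reproducible over six months. At 30 per arm the avoidable variance can matter, and the data needed to remove it are already scheduled.

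**Working it through.** **Inputs from the documents.** 30 patients per arm (Section 3). FibroScan and lipids at the first visit in both arms (Sections 1 and 2). The planned total of 60 is stated without any basis, so there is no sample-size calculation to reproduce.

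**Inputs assumed.** Two-sided alpha 0.05; 80% as reference power; equal standard deviations at first visit and follow-up, set to 1; no dropout; rho from 0.3 to 0.9.

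**Step 1: variances of the between-arm contrast.**
- Change score: 2(1 − rho) × 2/30
- ANCOVA: (1 − rho²) × 2/30
- Ratio: (1 − rho²) / [2(1 − rho)] = (1 + rho)/2

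At rho 0.5 the variances are 1 × 0.0667 = 0.0667 and 0.75 × 0.0667 = 0.0500, so the standard errors are 0.258 and 0.224 SD. ANCOVA with 30 × 0.75 = 22.5 patients per arm would match the change score with 30.

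**Step 2: power.** By the normal approximation, the change score has 80% power when the effect is (1.960 + 0.842) = 2.802 of its standard errors. ANCOVA power for that same effect is Φ(2.802 / √[(1 + rho)/2] − 1.960). At rho 0.5 this is Φ(2.802/0.866 − 1.960) = Φ(1.275) = 89.9%.

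| rho | variance ratio | effect giving change score 80% (SD) | ANCOVA power | gain (points) |
|---|---|---|---|---|
| 0.3 | 0.65 | 0.856 | 93.5% | 13.5 |
| 0.4 | 0.70 | 0.792 | 91.8% | 11.8 |
| 0.5 | 0.75 | 0.723 | 89.9% | 9.9 |
| 0.6 | 0.80 | 0.647 | 87.9% | 7.9 |
| 0.7 | 0.85 | 0.560 | 86.0% | 6.0 |
| 0.8 | 0.90 | 0.457 | 84.0% | 4.0 |
| 0.9 | 0.95 | 0.323 | 82.0% | 2.0 |

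**Step 3: check of the approximation at rho 0.5, effect 0.723 SD.** The noncentral t with 58 and 57 degrees of freedom gives 78.7% against 88.9%. A simulation of 20,000 trials gives 78.6% against 87.9%, a gap of 9.3 points. If instead ANCOVA is set at 80% (effect 0.626 SD), the change score has 67.9%, a gap of 12.1 points.

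**Step 4: dependence on the true effect at rho 0.5.** The gap is 2.5 points at 0.2 SD, 9.1 at 0.4, 12.3 at 0.6, 10.5 at 0.7, 7.5 at 0.8 and 2.2 at 1.0. It is large only in the middle of the power range.

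**Step 5: where the lost precision comes from.** The baseline mean difference has standard error √(2/30) = 0.258 SD. At rho 0.5, an imbalance of one standard error moves the change-score contrast by (1 − 0.5) × 0.258 = 0.129 SD. The variance of that shift is 0.129² = 0.0167, exactly the difference 0.0667 − 0.0500 from Step 1. In general 2(1 − rho) − (1 − rho²) = (1 − rho)². Imbalance and lost precision are therefore the same quantity, counted once.

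**The case against.** The strongest objection is that the power figures concern an analysis the plan does not contain. A reader might infer that this plan, as written, loses about 10 points of power. The documents do not support that. The paired t test compares an arm with itself, so it has no between-arm power to lose, and the comparator in the table is a two-sample change-score test that no section specifies. The figures are conditional: they apply if the planned changes are contrasted between arms.

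A reader might also infer that chance imbalance biases the result. It does not: under randomisation the change-score contrast is unbiased, and its standard error already includes the imbalance component (Step 5). Given an observed imbalance the estimate is shifted, but that is the same loss seen conditionally.

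Three further limits stand:
- Section 3 names no instrument. That FibroScan measures the primary end point is inferred from Section 1, whose wording (fatty liver and fibrosis) differs from Section 3's (steatohepatitis and fibrosis).
- Section 3 does not say which visits are paired, or whether severity is continuous or graded. The formulae are for a continuous outcome.
- With five follow-up FibroScans scheduled, a model of follow-up on baseline is not a single primary analysis until a visit is named.

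It can also be said that this is only a detail of the larger gap, the missing between-arm test. The two are closely linked and one sentence can repair both. The detail still merits stating, because a sponsor told only to add a between-arm test could choose the change score.

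**Conclusion.** The point holds in conditional form. First-visit values are collected in both arms, and no baseline-adjusted supplement-versus-placebo estimate is planned. Relative to a between-arm contrast of the planned changes, ANCOVA would cut the variance to (1 + rho)/2. Where that contrast has 80% power, this is worth about 2 points (rho 0.9) to 13.5 points (rho 0.3), and about 10 at rho 0.5. The size rests on assumed rho, equal standard deviations, assumed effects and no dropout. The direction does not depend on the value of rho, since ANCOVA's large-sample variance is never above that of the change score. At rho 0.8 or higher the gain is 4 points or less, so this is a worthwhile improvement at almost no cost. It does not show that the trial is underpowered, on which the documents give no basis for a judgement.

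**What to change.** In Section 3, state that the primary analysis of each continuous FibroScan outcome (steatosis and stiffness) is a linear model of the week 24 value on randomised group plus the first-visit value of the same outcome. Report the adjusted supplement-minus-placebo difference with a 95% confidence interval. Week 24 is suggested because it is the last scheduled visit and closes the six-month treatment period. Say explicitly that these FibroScan outcomes are the primary measures.

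Use the same form for each lipid, with its own first-visit value as covariate. I do not extend this to weight, for which the schedule shows no measurement. Keep the paired t test as a descriptive within-arm summary.

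The cost is a sentence or two of text and one linear-model call per outcome in the R software already named. It uses one residual degree of freedom (60 − 3 = 57 instead of 60 − 2 = 58) and needs no extra patients, visits or measurements.
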